Aim 4. Pilot test and refine interview procedures and guide. Recruit 75% of interview respondents. Complete 50% of interviews. Ongoing transcription and create coding scheme for interview analysis.

Months 13-18 Additional refinement of protocols with Advisory Panel input and DBSA community feedback.

Aims 1-3. Finalize Aim 1 main analyses and draft **manuscripts 1 and 2** reporting changes in access to appropriate outpatient treatment and quality of care. Additional dissemination activities. Preliminary Aim 2 analyses of changes in adverse patient outcomes (psychiatric/non-psychiatric ED visits and hospitalizations) following switching to HDHPs. Contrast HDHP members with and without full drug cost-sharing. Early dissemination of Aim 2 results through conference abstract submissions, additional stakeholder meetings, and DBSA avenues of communication.

Aim 4. Refine coding for interview analysis. Completion of remaining interviews, attaining theme saturation. Ongoing transcription and analysis of interviews. Early dissemination of interview findings through conference submissions, stakeholder meetings, and DBSA avenues of communication.

Months 19-24 Additional refinement of protocols with Advisory Panel input and DBSA community feedback.

Aims 1-3. Finalize Aim 2 main analyses and draft **manuscript 3** reporting changes in adverse patient outcomes (psychiatric/non-psychiatric ED visits and hospitalizations) following switching to HDHPs. Additional dissemination activities from Aim 2. Preliminary Aim 3 analyses of changes in patient out-of-cost burden. Stratify analyses contrasting HDHP members with and without full drug cost-sharing. Early dissemination of Aim 3 results through conference abstract submissions, additional stakeholder meetings, DBSA avenues of communication.

Aim 4. Finalize analyses of interviews and draft **manuscript 4** on patient perspectives on access to

appropriate treatment of bipolar in the context of commercial plans. Dissemination of results.

Months Additional refinement of protocols with Advisory Panel input and DBSA community feedback.

25-30 **Aims 1-3.** Finalize Aim 3 main analyses and draft **manuscript 5** reporting changes in patient out-of-cost burden following switching to HDHPs. Additional Aim 3 dissemination activities. Conduct stratified analyses for Aims 1-3 by vulnerable subgroups (race/ethnicity, SES, rural residence, comorbidity burden). Early dissemination of results of stratified analyses through conference abstract submissions, additional stakeholder meetings, DBSA avenues of communication.

Aim 1-4. Develop framework for **manuscript 6** on our study's experiences in patient engagement.

Months Ongoing inputs from Advisory Panel and DBSA community feedback, including recommendations for future policy and research. Prepare and submit final report; final dissemination activities.

31-36

Aims 1-3. Finalize analyses of disparities in outcomes (Aims 1-3) following switching to HDHPs among particularly vulnerable subgroups (race/ethnicity, SES, rural residence, comorbidity burden). Draft **manuscript 7** on disparities in outcomes; additional dissemination activities.

Aim 1-4. Draft **manuscript 6** on our study's experiences in patient engagement.

E. PATIENT POPULATION [RQ-3; PC-2]

E.1 Populations Affected: Aims 1-3 analyze retrospective de-identified data from 2004-2014 insurance claims. The characteristics and numbers of insurance plan members whose claims data will be analyzed in Aims 1-3 are described in Sections C.2, C.5, and C.10. We seek to determine the impacts of switching to HDHPs within the insured population that yielded these claims. This population is very minimally affected by the research itself because we are observing events that took place in the recent past, and the data have been de-identified. However, people living with bipolar illness and their families have significant potential to benefit when our study findings are disseminated, in terms of better public understanding of the challenges these patients face, and improvements in health system policies.

In **Aim 4**, interview respondents will voluntarily share their experiences on treatment of bipolar disorder in the context of commercial insurance coverage. Following DBSA recruitment efforts, we will contact ~100 individuals to potentially participate in the study, and we plan to interview up to 60 patients or family members representing a range of geographic locations, both genders, patients aged 12-64, different race/ethnicities, and levels of socioeconomic status. Through the interview process, respondents may develop deeper awareness of the attendant issues of insurance coverage and treatment choices, or they may experience mild emotional distress discussing sensitive topics, but we expect no significant impacts on this population (see Protection of Human Subjects). Our analyses will emphasize answers to the following types of questions: "Does your insurance help you pay for therapist visits?", "How did you learn about these aspects of your coverage?", and "When you have to make difficult choices, what do you prioritize?"

Patient partners in our study will participate as equals on our team and, hopefully, derive net benefits in terms of collegiality, learning, and compensation. The broader population of the DBSA community (i.e., users of DBSA social media, etc.) and patients and stakeholders in the public at large will be able to learn about study results and provide feedback (see Section G), but these would not differ substantially from the effects of existing DBSA outreach activities and routine publication of research.

F. RESEARCH TEAM AND ENVIRONMENT

Our proposed study will assess how patients with bipolar disorder fare when required to pay much higher out-of-pocket costs under HDHPs. It will be conducted primarily at the Department of Population Medicine (DPM), which resides within the Harvard Pilgrim Health Care Institute (HPHCI), and is a department of Harvard Medical School. The study capitalizes on DPM's expertise using administrative data and strong quasi-experimental study designs to evaluate the impacts of cost-containment and coverage policies on medical and psychiatric outcomes. We have conducted both early regional and ongoing large national HDHP studies analyzing health care utilization, costs, and outcomes in general health populations and populations defined by somatic conditions. Our experience with rigorous designs and innovative methods will produce reliable,

[name]

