A.3. High-Deductible Health Plans in the US are Expanding at Unprecedented Rates [*RQ-5*]: The US has been grappling for decades with rising health spending, which outpaces inflation and is often cited as a threat to the economic sustainability of governments, employers, and families.²⁰ In response, payers²¹ and employers²² have increasingly turned to high-deductible health plans (HDHPs) with high levels of patient cost-sharing. Compared with traditional plans, HDHPs have lower monthly premiums, but they subject most services to annual deductibles of \$2,600 to \$12,900 per family.²³ Families might therefore pay the entire deductible amount out-of-pocket before more generous coverage, such as full coverage or coinsurance, begins.

Two types of HDHPs predominate in the US: Health Savings Accounts (HSA) eligible and HSA-ineligible HDHPs. The 2003 Medicare Modernization Act created HSAs that allow employers and employees to contribute tax-free funds into accounts for medical services payments.²⁴ Such accounts must be connected to HDHPs that have a regulated structure including minimum deductible amounts, maximum annual account contributions, and defined coverage requirements. HSA-eligible HDHPs with "value-based" out-of-pocket exclusions often fully cover a limited number of preventive services (e.g., cancer screening), have a moderate copayment (e.g., \$20) for annual primary care physician preventive visits, but require full cost-sharing up to the annual deductible for all other services (e.g., mental health visits, medications, tests, hospitalizations). In contrast, HSA-ineligible HDHPs (i.e., Health Reimbursement Arrangement plans or those without an associated account) are also designed to be "value-based," but generally include more generous drug coverage (i.e., relatively low medication copayments as in traditional plans) and specialist visits might be exempt from the deductible; most other services including mental health visits and hospitalizations are subject to the deductible.

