B.3. Pathways toward Improvements in Care [RQ-3]: HDHPs could cause disruptions in treatment of bipolar illness due to cost-related nonadherence or confusion about coverage details. HDHPs could also cause reductions in outpatient and inpatient care, or increased psychiatric hospitalizations due to treatment disruptions. Because of the rapid growth in HDHPs, our study is highly relevant to policymakers at all levels. Both types of HDHPs (with and without medications subject to the deductible) as well as traditional plans with no deductible are all highly prevalent in the US. This wide “practice variation” in insurance benefits design implies a crucial need to understand the impacts of design differences in order to optimize patient health. Prior research indicates that even small differences in insurance design can have powerful consequences for vulnerable patients.

Opportunities to implement policy recommendations would be readily available. Insurers redesign benefit offerings every year and respond quickly to shifting pressures from employers. Our study potentially includes an immediately-available “policy intervention,” if HDHPs with generous medication coverage promote bipolar medication adherence and better health outcomes, employers and health insurers could quickly shift to such designs. Evidence that exempting mood stabilizing drugs from full cost-sharing preserves appropriate utilization could also contribute to amendments to the 2003 Medicare Modernization Act that requires HSA-eligible HDHPs to subject all medications to the deductible.²⁴ State and federal regulators closely examine insurer practices and set standards for benefits packages. We expect that policy makers will use our results to introduce health plan designs that promote high quality care among patients with mental illness.

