To assess the efficiency of data linkage between claims data and credit report data and implications for bias based on proportion of total sample that may not have these data [IR-2], data vendor Optum will link patient addresses to geocoded 2000 and 2010 census data, a process that has previously yielded <1% unlinked data. Information on member race and ethnicity is also included, based on geocodes, US census data, and an imputation strategy incorporating member surname. [MD-2] We will also have detailed benefit information for ~80% of employers, including individual and family deductible levels, HDHP type (HSA, Health Reimbursement Arrangement, or non-account), and copay and coinsurance amount by service type. For employers with missing deductible levels, [MD-2] we have developed an imputation algorithm that has 97.0% sensitivity and 96.2% specificity. To determine employer deductible levels, we will use a benefits type variable that we have for smaller employers (with approximately 100 or fewer employees). For larger employers, we will take advantage of the fact that health insurance claims data are the most accurate source for assessing out-of-pocket obligations among patients who utilize health services. Our claims data contain an in-network/out-of-network deductible payment field. For patients who use expensive or frequent services, the sum of their yearly deductible payments will add up to clearly identifiable exact amounts such as \$500.00, \$1000.00, \$2000.00, etc. When several members have these same amounts, it provides strong evidence that the employer offered such an annual deductible level. It will also be possible to detect employers that offer choices of deductible levels when multiple employees have deductibles at two or more levels, such as 20 employees with an annual amount of \$1000.00 and 12 employees with \$500.00. For employers with at least 10 workers, we therefore will sum each employee's in-network deductible payments and number of claims over the enrollment year and plan to assess other key characteristics such as percentage with Health Savings Accounts. On a randomly selected half of the employer data set that contained our calculated employer characteristics (such as the percentage of patients with deductible levels between \$1000-\$2500) as well as actual deductible amounts, we will use a logistic model that predicts the 3-level outcome of deductible <=\$500/\$500-\$999/>\$1000 based on multiple aggregate employer characteristics such as the first and second most common whole number deductible value, the percentage with Health Savings Accounts or Health Reimbursement Arrangements, the median deductible payment, the percentage of employees using services, the employer size, the percentage of employees with deductible levels between \$100-\$500/ \$500-\$1000/ \$1000-\$2500/ >\$2500, etc. This predictive model will output the probability that employers had deductibles in the three categories (summing to 1) and we will assign the employer to the level that had the highest probability. If we detect employers that had 10 or more employees with whole number deductible levels both above and below \$500 (e.g. \$250.00 and \$1500.00), we will assign the employers' category as "choice." If 100% of employees had Health Savings Accounts, we will overwrite any previous assignment to classify the employer as a high-deductible employer. We will test the predictive model on the other half of the sample for which we have actual deductible levels. At employers with 75-100 workers, we anticipate to find sensitivity and a specificity of over 96%. We will have all study years (2004-2014) available in-house. The sample size (see section C.10) will be sufficient to investigate HDHPs' effects within carefully selected employer groups, as well as within vulnerable patient subgroups.

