
Our patient partner, DBSA, will help recruit **Aim 4 interview respondents** through local chapter meetings and social media platforms. Interested individuals will contact DBSA, who will screen for eligibility. Participants will be non-elderly adult patients with bipolar illness enrolled in commercial plans or caretaking family members, able to converse in English; respondents will give informed consent for recorded telephone interviews of approximately 1 hour, each conducted using a semi-structured interview guide.

C.3 Interventions and Comparators [RQ-5; HT-1 to HT-4]: Our analyses in **Aims 1-3** will include members of traditional health plans (including low-deductible Health Maintenance Organization, Preferred Provider Organization, and Point of Service plans) and HDHPs. We define traditional health plans as those having annual deductibles of \$500 or less for individuals and copayments of less than \$50 for most services. We

[name]

define HDHPs as those requiring individuals to spend at least \$1000 out-of-pocket annually for most clinical services before more comprehensive coverage begins, but which typically have exemptions for preventive care.

[figure not shown]
We will further classify HDHPs as HSA-eligible and HSA-ineligible. HSA-eligible HDHPs subject most medical services (including psychotropic medications and all mental health visits) to the annual deductible; only “preventive” health care (a limited set of services such as check-ups and screenings) are under first-dollar coverage, either for free or with a modest copayment. By contrast, HSA-ineligible HDHPs also subject many services to the deductible, but they generally include more generous coverage for medications (i.e., tiered copayments, as in traditional plans) and primary care visits might require only a modest copayment. These coverage differences for key services create a natural experiment that will permit us to answer crucial questions regarding optimal insurance designs for patients with bipolar illness.

For **Aim 4** in-depth interviews, we will sample respondents with either traditional insurance or HDHPs in order to explore this contrast. However, we recognize that many respondents may not fully understand the design of their insurance plan, and we expect new themes to emerge regarding lack of benefits clarity.

C.4 Enrollment Period and Follow-up Duration for Aims 1-3:

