Study cohort: Of 41,638,597 members enrolled in the national insurer during 2004-2012, we found 18,184,556 have a 2-year enrollment span, a study inclusion criterion. Among these, 148,706 have at least 1 inpatient or 2 outpatient diagnoses of bipolar disorder; this reflects a prevalence of 1% members with bipolar disorder, which is consistent with expectation among the commercially insured population. Among 148,706 members with bipolar disorder, 57,028 matched our age criterion (12 to 64 years of age). (We will conduct sensitivity analyses of our main results varying our bipolar diagnosis criteria [e.g., requiring diagnosis prior to index date, requiring only one diagnosis; [CI-5](#)]) To minimize selection bias, our study cohorts will include individuals whose employers offer only a single benefit type with no choice. Our intervention cohorts will include traditional plan members with bipolar illness who experience an employer-mandated switch to HSA-eligible HDHPs with full drug cost-sharing (i.e., out-of-pocket medications payments until the deductible limit is reached), or to HSA-ineligible HDHPs that subject medications only to copayments as in traditional health plans. The control cohort will include members with bipolar illness whose employers offered only a traditional plan for the follow-up year. We estimate that 7,227 have HDHP insurance and 49,801 have traditional plan insurance. **Exclusion Criteria:** We will exclude members age 65 years or older who could be eligible for Medicare benefits, including drug coverage through Medicare Part D. We will also exclude members whose employer offered a choice of health plan. This strengthens our design by reducing potential selection bias due to, for example, healthier members selecting HDHPs or individuals anticipating discretionary utilization. . Input from our panel advisory meetings led to the decision to exclude from our cohort those individuals with a diagnosis of schizoaffective disorder or schizophrenia in order to identify a clinically homogenous group for our study, as advised by our clinical psychiatrist co-investigator [name]. This criterion was further supported by our advisors at DBSA. According to sources at DBSA, schizophrenia and schizoaffective disorder are not comorbidities seen in their peer population. In their judgment, people living with schizophrenia and schizoaffective disorder are unlikely to come to DBSA meetings and would have their needs better met in other settings. The ineligibility criteria therefore included the 3 categories: 1) patients with only 1 outpatient bipolar diagnosis, 2) 1 inpatient or 2 outpatient diagnosis of schizophrenia diagnosis, and 3) 1 inpatient or 2 outpatient diagnosis of schizoaffective disorder. We estimate 3,731 individuals were excluded from the study cohort due to evidence of schizoaffective disorder and schizophrenia. There have been no changes in identifying eligible individuals to enroll in our approved research plan beyond the stakeholder advisory panel decision to exclude schizoaffective disorder and schizophrenia, calculate their overlap with the bipolar population, and exclude them from the final cohort.

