C.9 Analysis Plan for Aims 1-3 [IR-3; HT-1 to HT-4]: Overview: These analyses will determine how specific outcomes change after employer-mandated switching from traditional plans to HDHPs. To address methodological standard IR-3, we plan to use the most rigorous quasi-experimental retrospective longitudinal designs and analyses available for AIMS 1-3, namely interrupted time series with comparison series matched on multiple baseline covariates as well as the baseline trend of outcome measures. For Aim 4 we will use appropriate standard techniques for qualitative analyses of interview data (detailed below). We will first compare the characteristics of our matched cohorts (HSA-eligible and HSA-ineligible HDHP members, and traditional plan controls) using chi-square tests, t-tests and Poisson or quantile regression.¹²⁶ We will contrast sociodemographic characteristics, employer characteristics, and baseline health care utilization. Subsequent analyses will use time-series plots and rigorous analytical methods appropriate for each outcome, described below. Data collected on the same individuals in successive years are correlated (“repeated observations”). The extended general linear models—generalized estimating equations (GEE) and generalized linear mixed models (GLMM) for binary, count, or continuous measured outcomes—are appropriate methods for estimating parameters to adjust for these correlations within subjects.^{82,83} The term of interest in our GEE or GLMM models will be the interaction between *time* (pre versus post) and *cohort* (HDHP versus traditional plan). Statistical analyses in Aims 1-3 will first compare those transitioning to HDHPs with patients remaining in traditional plans; then contrast effects between HDHP members with full drug cost-sharing (HSA-eligible plans) and those transitioning to HDHPs without full drug cost-sharing (HSA-ineligible HDHPs). Each HDHP group will have as controls only those traditional plan members paired to a given HDHP member during the propensity score match. To examine possible selection effects due to applying our enrollment criteria and propensity matching approaches (see C.10), we will also compare our analytic population to members with bipolar disorder who were excluded from the sample.^[MD-4; CI-2]

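### The comparison of HDHPs with and without drugs under the deductible is built on HSA status, which the plan says tracks drug coverage only in general, and no step checks it

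*Combined protocol and SAP*

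**What the plan says.** The study objective at the start of section C is to compare two HDHP types, with and without medications subject to the deductible, against traditional insurance.

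- **C.3 (classification rule):** "We will further classify HDHPs as HSA-eligible and HSA-ineligible". On the second group it adds: "but they generally include more generous coverage for medications (i.e., tiered copayments, as in traditional plans".
- **A.3 (background):** the same qualification, "but generally include more generous drug coverage (i.e., relatively low medication copayments as in traditional plans".
- **C.5 (intervention cohorts):** no qualification. Members switch to HSA-eligible plans with full drug cost-sharing "or to HSA-ineligible HDHPs that subject medications only to copayments as in traditional health plans".
- **C.9 (analysis):** after HDHP versus traditional, the analysis will "then contrast effects between HDHP members with full drug cost-sharing" (HSA-eligible plans) and "those transitioning to HDHPs without full drug cost-sharing (HSA-ineligible HDHPs".
- **B.3:** the 2003 Act "requires HSA-eligible HDHPs to subject all medications to the deductible", so HSA-eligible plans all have drugs under the deductible as the plan describes it.
- **C.2 (benefit data):** for about 80% of employers these include "HDHP type (HSA, Health Reimbursement Arrangement, or non-account), and copay and coinsurance amount by service type". Pharmacy is not named as a service type. The imputation for the remaining employers covers the deductible level only.
- **C.7, Aim 3:** deductible, coinsurance and copayment amounts will be summed separately for prescription fills.
- **C.10:** the projected HDHP sample is 10,800, made up of 1,525 HSA and 9,275 non-HSA members.

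**The concern.** The exposure in the question is whether drugs fall under the deductible. The exposure in the analysis is HSA status. On the HSA-eligible side the two coincide, by the statute as B.3 describes it. On the HSA-ineligible side the plan itself says they coincide only as a rule.

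An HSA-ineligible plan that puts drugs under the deductible would sit in the arm labelled as having no full drug cost-sharing. The error runs one way and draws the two HDHP arms together. At stake is the finding that B.3 puts forward as ready for policy use: whether exempting mood-stabilising drugs from the deductible preserves treatment. A diluted contrast could be read as showing that the exemption makes little difference. The sensitivity analyses described concern the bipolar diagnosis criteria (C.5) and missing socioeconomic data (C.8); none varies the drug-benefit classification.

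**Working it through.** **1. Is the copayment-only description in C.5 applied as a filter?** C.10 gives 1,525 + 9,275 = 10,800, the whole projected HDHP sample. No group is set aside for HSA-ineligible plans with drugs under the deductible. C.9 equates HSA-ineligible with no full drug cost-sharing and adds no condition. No filter is therefore visible.

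**2. Nearest stated figure.** The plan gives no power for HSA versus non-HSA. C.10 does give 80% power for psychiatric hospitalisation, 10% versus 8%, with 2,160 HDHP members and 8,640 controls. A two-proportion normal approximation at two-sided 0.05 gives 0.82, so the figure reproduces. The same formula is used in step 4.

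**3. Dilution.** Let a be the effect with drugs under the deductible and b the effect without. Let m be the share of HSA-ineligible members with drugs under the deductible, assumed to respond as HSA-eligible members do. Then

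- expected effect in the HSA-ineligible arm = m·a + (1 − m)·b
- observed contrast = a − [m·a + (1 − m)·b] = (1 − m)(a − b)
- sample-size inflation for equal power ≈ 1/(1 − m)²

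The documents give no m. The rows below are assumptions, applied to the 3-point adherence difference used in C.10 (49% to 46%).

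| m (assumed) | Members in the wrong arm (9,275 × m) | Contrast kept | 3 points appear as | Inflation |
|---|---|---|---|---|
| 5% | 464 | 95% | 2.85 | 1.11 |
| 10% | 928 | 90% | 2.70 | 1.23 |
| 20% | 1,855 | 80% | 2.40 | 1.56 |

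**4. Illustrative power.** The plan's hospitalisation rates (8% versus 10%) are applied to the two HDHP arms, ignoring matching and repeated measures. As planned, the comparison is 1,525 versus 9,275 with the second rate diluted to 10% − 2m points. With misplaced members removed, it is 1,525 versus 9,275(1 − m) at the undiluted rates.

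| m (assumed) | Power as planned | Power, misplaced members removed (arm size) |
|---|---|---|
| 0 | 0.70 | 0.70 (9,275) |
| 5% | 0.65 | 0.70 (8,811) |
| 10% | 0.61 | 0.69 (about 8,348) |
| 20% | 0.51 | 0.68 (7,420) |

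For adherence treated as binary (46% versus 49%), power at m = 10% is 0.50 as planned and 0.58 with the members removed. Removal costs little because the HSA arm is the smaller one and limits precision.

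**5. Restricting to employers with benefit data.** If 80% of employers means 80% of members, 1,220 versus 7,420 remain, and hospitalisation power with no misclassification is 0.60. Dropping every employer without benefit data gains power only if m exceeds 1 − √0.8 ≈ 11%, although it removes the bias from misclassification at any m. Employers without a recorded drug benefit are better classified from claims than dropped.

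**The case against.** **C.5 may be an inclusion rule.** Its clause is restrictive in form and parallels the wording for HSA-eligible plans. On that reading the misplaced plans are excluded and m is zero. The reading is possible, but nothing in C.9 or C.10 carries it out, so the point stands as a need to reconcile and apply the rule.

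**The loss is conditional.** A reader might infer that the contrast is diluted by a known amount. The documents do not support that: they give no share, and it could be small.

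**The data are not all in hand.** A reader might also infer that the drug benefit is recorded and merely unused. C.2 promises benefit detail for about 80% of employers and mentions neither pharmacy nor a field for whether drugs fall under the deductible. What can be said is that Aim 3 already needs deductible amounts on prescription fills, and C.2 already infers employer deductibles from claims.

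**Claims-based classification can itself bias.** A patient who fills nothing, or meets the deductible through medical care, shows no deductible payment on drugs. Classifying from the study patient's own fills after the switch would make exposure depend on adherence, which is an outcome. This objection is sound and determines how the fix must be done.

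**HSA status matters in its own right.** The policy lever in B.3 is the HSA statute, so that comparison deserves to be kept, labelled as what it is. Aim 3 would also show drug cost per fill in each arm, which could reveal poor separation, but the plan does not say it would be used that way.

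**Conclusion.** The concern holds for one comparison. The contrast between HDHPs with and without drugs under the deductible rests on a proxy that A.3 and C.3 qualify, that C.5 and C.9 treat as exact, and that no step verifies. The contrast falls to (1 − m) of its true size, or 95% to 80% for an assumed m of 5% to 20%. This assumes that HSA-ineligible members with drugs under the deductible respond as HSA-eligible members do.

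All HDHPs versus traditional plans is unaffected. HSA-eligible versus traditional is unaffected too, given the statute as B.3 describes it. Correct classification would still not isolate drug cost-sharing, because A.3 and C.3 indicate that the two HDHP types can also differ in accounts and visit coverage.

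**What to change.** 1. Reconcile A.3, C.3, C.5, C.9 and C.10. State whether the copayment-only description in C.5 is an inclusion rule and, if so, how it is applied and what it does to the 9,275.
2. Classify each HSA-ineligible employer's drug benefit from the benefit file where it is recorded. Otherwise use deductible payments on pharmacy claims pooled over all the employer's members, never the study patient's own fills.
3. Use only HSA-ineligible employers with drugs outside the deductible as the arm without full drug cost-sharing.
4. Report how far the observed drug benefit agrees with HSA status, which supplies m.
5. As sensitivity analyses, give the contrast by HSA status as now planned, and with the reclassified plans added to the full-cost-sharing arm. Under the assumed 5% to 20% that arm would grow from 1,525 to 1,989–3,380 (1,525 + 464 to 1,525 + 1,855), but it would mix plans that differ in accounts and possibly in visit coverage.

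The cost is some programming on data the study already plans to use, a few employers that stay unclassifiable, and a somewhat smaller HSA-ineligible arm. The remaining differences between HDHP types should be stated as a limitation.
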